#### 4.7. Pharmacodynamic Analyses

The PD effects of ALXN1210 administered IV will be evaluated as follows:

- Changes and percent changes in serum Total C5 and Free C5 concentration over time.
- Change and percent change in cRBC hemolysis over time.
- ALXN1210 concentration required for complete terminal complement inhibition based on PD effects evaluated.

PD data will be listed for each individual subject and absolute (observed values) as well as changes and percent changes from baseline will be summarized at each time point by treatment dose using the following descriptive statistics.

- N (the number of subjects)
- Arithmetic mean
- SD
- Median
- Minimum
- Maximum.

Individual percent change from baseline versus actual time and mean percent change from baseline versus nominal time will be presented for each PD parameter.

## 4.8. Immunogenicity Analyses

Immunogenicity, as measured by anti-drug antibodies, will be summarized in tabular form (number and percentage of subjects developing ADA) by treatment dose and will be presented in by-subject listings.

Immunogenicity data will be listed for each individual subject and will be summarized at each time point by treatment dose using the following descriptive statistics, if applicable.

- N (the number of subjects)
- Arithmetic mean
- SD
- Median
- Minimum
- Maximum.

### 4.9 Methods for Withdrawals, Missing Data, and Outliers

The individual serum concentration data, and the actual time for IMP administration and blood sampling will be used throughout the analyses. If there is any doubt in the actual time a sample is taken, then the scheduled time will be used. For PK data analysis, please see Section 4.5 Pharmacokinetic Analysis for the handling of missing and BLQ values. For PD data analysis, there will be no imputation for missing values.

If medication dates are incomplete and it is not clear whether the medication was concomitant, it will be assumed to be concomitant.

AEs with unknown start date/time will be assumed to be treatment-emergent unless the end date/time is known to be before the first administration of IMP. Otherwise missing or partial dates will be listed as such.

There will be no further imputation of missing data i.e. subjects who prematurely discontinue from the study will not be included in summary statistics or analyses beyond the time of discontinuation. If a subject is withdrawn from study treatment but continues to participate in the study, the data collected will be included according to the treatment initially received for the Safety set.

Depending on the extent of missing values, the appropriateness of the methods described for handling missing data may be reassessed prior to database lock (to examine the sensitivity of results to handling of missing data).

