8. INVESTIGATIONAL PLAN

8.1. Overall Study Design

This is a Phase 1, open-label, single ascending and multiple set dose study designed to evaluate the safety, tolerability, immunogenicity, PK, and PD of ALXN1210 in healthy Japanese subjects.

All subjects are to be screened for eligibility in the study after providing written informed consent to participate. Subjects who fail to meet eligibility criteria may not be rescreened for participation in the study, unless the condition that led to eligibility failure is transient, self-limited, and easily treatable, and is expected to be resolved at the time of dosing, as agreed by the investigator and medical monitor.

A total of 3 cohorts and up to 16 subjects are planned for evaluation. The cohorts will be enrolled sequentially and all subjects will receive IV ALXN1210:

[figure not shown]
- Cohort 1, 400 mg single dose (N = 4)
- Cohort 2, 800 mg single dose (N = 4)
- Cohort 3, 800 mg Q4W for a total of 5 doses (N = 6 to 8)

A Safety Review Committee (SRC) will conduct a review of the available clinical and safety data after the last subject in the 400 mg cohort (Cohort 1) has completed Day 15 to determine if dose escalation to 800 mg may proceed (Cohort 2). The SRC will conduct a review of all available clinical and safety data after the last subject in the 800 mg cohort (Cohort 2) has completed Day 15 to determine if dosing in Cohort 3 may begin. Dose escalation to the multiple repeated dose phase will proceed as scheduled and the study will continue as long as no prespecified toxicity events occur (see Table 3). Dose continuation within Cohort 3 after Period 2 will proceed following review of the available safety and tolerability data by the PI in accordance with the protocol's toxicity rules. Minimum data requirements do not apply for the PI review; however, it is expected to include available data up to 14 days after each dose.

Up to 2 subjects per cohort may be added if 2 or more subjects discontinue before Day 15 (first dose only for Cohort 3) for reasons other than drug-related AEs, and after consultation with the SRC. All enrolled subjects will be included in analyses as appropriate. Subjects who have been dosed and who withdraw from the study will be followed for safety assessments through the last study visit, if possible.

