¹ Permissible windows for study assessments are described in the Study Operations Manual (SOM).

² Signed and dated EC-approved ICF must be obtained before any study-specific screening procedures are performed.

For subjects who do not have adequate documentation of prior MCV4 immunization or serogroup B vaccination, MCV4 immunization will be performed at least 56 days prior to first dose on Day 1, and vaccination for serogroup B meningococcal infections will be administered at least 56 days prior to Day 1 dosing with a booster administered at least 28 days prior to dosing on Day 1.

⁴ Complement activity, confirmed by a suitable assay such as complement alternative pathway (CAP) ELISA/C5 (hemolysis) inhibition, will be performed at screening to confirm subjects do not have a complement deficiency.

The CH50 sample drawn on Day -1 will be stored for future analysis should all the post-dose samples indicate that complement has not normalized.

Table 7: Schedule of Assessments: Cohort 3; Screening, Doses 1 to 4 (Refer to Table 8 for Period 5 and Follow-up) (Continued)

⁶ Height at Screening only.

See Table 9 for pharmacokinetics, pharmacodynamics, immunogenicity, infusion site evaluation, vital signs, and ECG collection time points required on each dosing day.

9 Continuous cardiac registration predose through the duration of infusion.

¹³ Collection of AEs and SAEs will begin after the ICF is signed.

Serum pregnancy test at Screening and urine pregnancy test as indicated for all female subjects. Positive urine pregnancy results should be confirmed by serum test.

¹⁰ Clinical safety laboratory measurements on Day 1 Period 1 will be collected 4 hours post dose. Follicle-stimulating hormones and estradiol levels will be measured at screening to confirm postmenopausal status, as described in Section 16.1.6.2.

Subjects who discontinue from the study before Dose 5 will be followed for 185 days after the last dose and instructed to return for follow-up visits (see Table 9). Subjects who discontinue the study after Dose 5 will be instructed to return for study visits through Day 298.

¹² Induration or reaction < 1 cm will not be listed as an AE unless it persists for more than 24 hours. Pain at site of infusion will be assessed using a visual assessment scale (0-10).

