- Subjects will be provided a safety card with information for healthcare provider and participant on symptoms of meningitis infection and contact information. This information will be reviewed with the subjects on a regular basis throughout the study (as indicated), and on the day of discharge.

Table 9: Cohort 3: Follow-Up and Early Termination Procedures for Subjects Who Discontinue During Periods 1 to 4

Days Relative to Last Dose	28	35	42	49	56	70	84	112	140	168	185	ET
Dose 1 Study Day	29	36	43	50	57	71	85	113	141	169	186	
Dose 2 Study Day	57	64	71	78	85	99	113	141	169	197	214	
Dose 3 Study Day	85	92	99	106	113	127	141	169	197	225	242	
Dose 4 Study Day	113	120	127	134	141	155	169	197	225	253	270	
Status (OP or CRU)	OP	OP	OP	OP	OP	OP	OP	OP	OP	OP	OP	OP
Assessments ¹												
Pregnancy test ²										X	X	X
Physical examination	X				X			X		X	X	X
Vital signs	X	X	X	X	X	X	X	X	X	X	X	X
ECG (triplicate)										X	X	X
Chemistry	X				X			X		X	X	X
Hematology	X				X			X		X	X	X
Coagulation	X				X			X		X	X	X
Urinalysis and urine chemistry	X				X			X		X	X	X
$\mathrm{CH}50^3$								X		X	X	
PK samples	X	X	X	X	X	X	X	X	X	X	X	X
PD panel (serum C5, cRBC hemolysis)	X	X	X	X	X	X	X	X	X			X
Immunogenicity (ADA)	X				X		X	X	X	X	X	X
Concomitant medications				←	Monito	red contir	uously	\rightarrow				X
Adverse events		•		←	Monito	red contir	uously	\rightarrow	•			X
Antibiotic prophylaxis ⁴				←	Daily unti	il CH50 no	ormalizes -	·				
Discuss safety risks with subject ⁵	X	X	X	X	X	X	X	X	X	X	X	X

Abbreviations: ADA = antidrug antibody; CRU = clinical research unit; ECG = electrocardiogram; ET= Early Termination; ICF = informed consent form; OP = outpatient; PD = pharmacodynamic.

¹ Permissible windows for study assessments are described in the SOM.

² Urine pregnancy test for all female subjects. Positive urine pregnancy results should be confirmed by serum test.

³ CH50 samples will be taken 112, 168, and 185 days relative to last dose. Once a normal CH50 result is obtained, antibiotic prophylaxis can be stopped and additional CH50 samples are not required; if the CH50 sample 185 days after last dose is not normal, the baseline sample will be analyzed and the investigator will contact the subject regarding whether antibiotic prophylaxis must be further extended.

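### SAP 4.9 could leave safety and antidrug-antibody data collected after study discontinuation out of the summaries, because the protocol uses the same term for subjects it keeps following

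*SAP*

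**What the plan says.** SAP Section 4.9 opens its rule with "There will be no further imputation of missing data i.e" and goes on to say that "subjects who prematurely discontinue from the study will not be included in summary statistics or analyses beyond the time of discontinuation". The next sentence makes an exception: "If a subject is withdrawn from study treatment but continues to participate in the study, the data collected will be included", with the qualifier "according to the treatment initially received for the Safety set".

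The protocol uses study discontinuation for people it goes on observing:

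- Footnotes to Tables 7 and 8: "Subjects who discontinue from the study before Dose 5 will be followed for 185 days after the last dose".
- The same footnotes, for later leavers: "Subjects who discontinue the study after Dose 5 will be instructed to return for study visits through Day 298".
- Table 9, titled "Cohort 3: Follow-Up and Early Termination Procedures for Subjects Who Discontinue During Periods 1 to 4", sets out visits with safety, PK, PD and ADA assessments.
- Section 8.1, for all cohorts: "Subjects who have been dosed and who withdraw from the study will be followed for safety assessments through the last study visit, if possible".

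SAP Section 2.2 lists ADA incidence among the safety endpoints, and Protocol Section 16 counts ADA testing as a safety assessment. SAP Section 4.1, however, gives immunogenicity its own analysis population, alongside separate PK and PD populations.

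**The concern.** One phrase has two meanings. In the SAP, discontinuing from the study marks the point after which a subject contributes nothing to the summaries. In the protocol it marks the start of a scheduled follow-up. An analyst who applies the SAP rule with the protocol's vocabulary would cut off data that the study set out to collect.

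Safety and tolerability are the primary objective, and the safety endpoints are incidences and changes from baseline, which are reported in summary tables. Protocol Section 8.3 gives a half-life of 30.8 to 32.4 days in the earlier single-dose study. A subject who leaves 14 days after a dose is therefore less than half a half-life past it (14/30.8 = 0.45; 14/32.4 = 0.43), and later adverse events or ADA from that subject remain relevant. The study is open label, so the choice between readings should not be made with the data in view.

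**Working it through.** **Follow-up arithmetic.** Dosing days are 1, 29, 57, 85 and 113. Adding 185 gives Days 186, 214, 242 and 270, which match the last column of Table 9 for Doses 1 to 4. For Dose 5, 113 + 185 = 298, the last visit in Table 8. The protocol's 185 days is reproduced for every dose.

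**Which SAP sentence fits whom.**

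| Subject | Excluding sentence | Retaining sentence |
|---|---|---|
| Cohort 3, stops before Dose 5, attends Table 9 visits | Fits, by the protocol footnotes' wording | Fits, by what happens; names the Safety set only |
| Cohort 3, leaves after Dose 5 | Fits | Does not fit: no treatment left to withdraw from |
| Cohort 1 or 2, leaves after the full single dose | Fits | Does not fit, for the same reason |
| Cohort 1 or 2, infusion stopped, stays in follow-up | Does not fit | Fits; names the Safety set only |

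In the first row no order of precedence is given. In the second and third rows only the exclusion applies. In no row does the SAP say what happens to ADA, PK or PD under their own populations.

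**What is scheduled after discontinuation (Table 9).** There are 11 visits, from 28 to 185 days after the last dose, plus a separate early-termination column. They carry 11 vital-sign sets, 11 PK samples, 9 PD samples, 7 ADA samples, 5 physical examinations and safety-laboratory sets, 3 CH50 samples and 2 ECGs. Adverse events are monitored throughout.

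**Days affected on the literal reading**, for a subject who leaves 14 days after a dose (an illustrative assumption):

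- Cohort 3 before Dose 5: 185 − 14 = 171 days. All 11 Table 9 visits fall in this span, since the first is at day 28.
- Cohort 3 after Dose 5: 298 − 127 = 171 days. Table 8 has 6 ADA samples in that span (Days 141, 169, 197, 225, 253, 298).
- Cohort 1, leaving on Day 15: 120 − 15 = 105 days.
- Cohort 2, leaving on Day 15: 140 − 15 = 125 days.

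The Cohort 1 and 2 figures are upper limits, because Section 8.1 promises safety follow-up only where possible.

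**Weight of one subject.** 1/4 = 25% in Cohorts 1 and 2; 1/8 = 12.5% to 1/6 = 16.7% in Cohort 3.

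**The case against.** A reader might infer that the SAP discards everything after discontinuation and so biases adverse-event incidence downward. The documents do not support that.

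- The excluding sentence is introduced as an explanation of not imputing. It can be read as saying only that nothing is carried forward for people who have gone.
- The next sentence can be read to keep Safety-set data for Cohort 3 subjects who stop before Dose 5 and attend Table 9 visits. Protocol Section 10.3 and the title of Table 9 speak of stopping dosing or discontinuing during a period, which fits that reading.
- Stops for tolerability are described as stopping study drug (Protocol Sections 8.4.2 and 12.6), and Section 12.6 keeps subjects with a stopped infusion on the full visit schedule. These are the subjects most clearly retained, so a downward bias from them does not follow. The same section shows that the retaining sentence can apply in Cohorts 1 and 2.
- SAP Section 4.4 plans an analysis of all adverse events and defines treatment-emergent as after dosing, with no cutoff at discontinuation. SAP Section 5 puts all enrolled subjects in the listings.

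All of this stands, and it limits the point to a possible loss. It does not close the gaps. The words of the rule exclude subjects, not imputed values. The retaining sentence is silent on people whose dosing is complete and on everything outside the Safety set. The option in SAP 4.9 to reassess missing-data handling before lock depends on the extent of missing values, and these values are not missing.

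The objection also carries weight on PK and PD. A subject stopped after Dose 1 is 112 days past dosing on Day 113, when continuing subjects are at the trough before Dose 5. Aligning by time since last dose would instead pool 28 days after one dose with 28 days after five. Leaving such values out of the main Cohort 3 profile is defensible.

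**Conclusion.** The conflict is real and should be settled in the SAP before database lock. It is firmest for subjects who leave after completing their single dose or Dose 5, where only the excluding sentence fits, and for ADA, a listed safety endpoint that the exception does not name. For Cohort 3 subjects who stop before Dose 5 it is an unresolved overlap; under the retaining sentence none of their Safety-set data would be lost. PK and PD handling after discontinuation is unspecified.

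The size rests on two assumptions: that at least one subject leaves early and still attends follow-up, and that the analyst applies the excluding sentence as written. In cohorts this small, one such subject would visibly change an incidence. If nobody leaves early, or SAP 4.4 is taken to govern adverse events, the effect on the adverse-event tables is nil.

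**What to change.** Amend SAP 4.9 along these lines:

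- The cutoff for summaries and analyses is the end of data collection for the subject, not the date of discontinuation or withdrawal.
- All adverse-event, laboratory, ECG, vital-sign and ADA data obtained after that date, including Table 9 visits and post-withdrawal safety follow-up, enter the safety and immunogenicity summaries under the cohort received.
- Only visits that did not take place are treated as missing.
- PK and PD values obtained after discontinuation from Cohort 3 subjects who stop before Dose 5 are reported separately, by number of doses received and time since last dose, and are not pooled with the five-dose profile.

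The cost is a short text change and a small additional table or listing. No new data are needed.

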#### 4.10 Protocol deviations

A protocol deviation is defined as a lack of compliance with the protocol which may interfere with the outcome of the trial. The protocol deviations will be identified and reviewed throughout the study, reviewed by PI/Sponsor and graded as minor or major. The final review will be performed at the Data Review Meeting prior to database lock. The protocol deviations will be listed.

## 5. CONVENTIONS

All listings will be ordered by treatment and subject number and will include all enrolled subjects. All data will be presented by the dose level of treatment.

For all tables, except PK parameter tables, descriptive statistics for min, max will be presented with the same number of decimal digits as the original values, and with one more decimal digit than the original data for mean and median; standard deviation will be reported with 2 or more decimal digits than the original.

For PK, the individual and summaries of PK parameter results will be reported in 3 significant digits in the listings and in the tables with the following exceptions:

- Tmax will be presented as follows: individual minimum, and maximum values will be reported exactly as the raw data are reported
- % CV will be presented to 1 decimal place

Page layout of tables and listings in landscape mode will be produced in Microsoft Word. Details of page layout will be provided in the tables figures and listings (TFL) shell document.
